#### Lead Associate Investigator

[name]	RMD/CC	[name]	[contact]	[contact]
----------------	--------	---------------	--------------	-------------------

Human Research Protections Program Investigator and Staff Training:

For this protocol, the following "Just in time" human subjects protection training courses are required for investigators and staff: None

Total requested accrual: 100 subjects (80 TBI Patients and 20 healthy volunteers)

N = 26 Wait-list control

N = 27 Aerobic Exercise Intervention

N = 27 Rapid-Resistive Exercise Intervention

N = 20 Healthy Volunteer Controls

Project Uses Ionizing Radiation: Medically-indically-i	No [ ated only d only	☐ Yes (attach RSC/RDRC documentation)
IND/IDE Drug/Device/#	🗵 No	$\Box Yes (attach FDA documentation)$
Sponsor:		
Durable Power of Attorney	🗵 No	□ Yes
Multi-institutional Project	□ No	X Yes

Institution#1: Center for Neuroscience and Regenerative Medicine FWA #\_ A00001628\_\_\_\_\_ Date of IRB approval September 15, 2016 (attach IRB documentation)

Institution#2: Department of Veterans Affairs Medical Center, Washington DC FWA # A00002475\_\_\_\_\_ Date of IRB approval January 19, 2018 (attach IRB documentation)

Data and Safety Monitoring Board □ No ⊠ Yes - Monitor

[name]		
University Sports Medicine		
State University of New York at Buff	falo	
[name]		
Office [contact]		
e-mail: [contact]		
Technology Transfer Agreement Agreement type and number Collaboration agreement with DC	□ No CVAMC Expir	☑ Yes – see Appendix 12 ration Date4/19/2022_
Samples are being stored	□ No	🗵 Yes

Flesch-Kincaid reading level of consent form: 10.0

# Precis

# Objective

The broad objective of this study is to examine the effects of moderate and more intense aerobic exercise as an intervention on cognitive performance, physical functioning and health-related quality of life in patients with chronic (more than 12 months post-injury) traumatic brain injury (TBI). Importantly, structural and biological brain changes will be measured to examine whether functional outcomes are related to exercise-induced adaptations. It is hypothesized that in the chronic phase of persons with TBI, there will be improved: 1) cognitive function, 2) physical fitness and fatigue severity, 3) motor performance and balance, and 4) mood and depressive symptoms, in those that performed the exercise intervention compared to a control group. It is also hypothesized that these functional improvements will be related to exercise intensity, improved cortical connectivity, dopamine transmission gene scores, and blood biomarkers related to neuroand angio-genesis.

# **Study Population**

80 ambulatory adults with non-penetrating TBI will be enrolled. We will also enroll up to 20 healthy volunteers as a comparison group for some of the outcome measures. Subjects will be recruited from NIH, affiliated hospitals/clinics and the community.

# Design

Healthy volunteers will have a limited assessment that includes brain imaging, blood draw for genetic testing, and a subset of the cognitive and behavioral testing at a single time-point. All subjects with TBI will perform baseline assessments including cognitive and behavioral performance, brain imaging, fitness, motor and balance testing, and selected blood and genetic testing. Thereafter, subjects with TBI will be randomized to either a waitlist control, or one of two exercise conditions: 1) 30 minutes at a fast pace, moderate-intensity (rapid-resistive exercise; RET); 2) 30 minutes at higher-intensity (aerobic exercise; AET). Both exercise groups will perform the exercise on an elliptical trainer 3 times a week, for a session duration of 45 minutes including warm-up and cooldown. The RET group will focus on rapid reciprocal motion with minimal resistance, while the AET group will exercise at an elevated intensity known to produce an aerobic effect. After 12 weeks, all groups will repeat the baseline assessments (3 month followup). Following this assessment, the waitlist control group will be randomized to either RET or AET and the exercise groups will cease formal supervised exercise sessions. A third assessment visit will be performed after an additional 12 weeks (6 month followup).

# **Outcome Measures**

Cognitive performance will be tested and interpreted compared to norms. Performance on motor and balance tasks will be assessed with the Smart Balance Measurement System and the GAITRite System. Physical fitness will be determined by peak oxygen consumption and aerobic threshold as measured by pulmonary gas exchange during an exercise tolerance test on the treadmill. Structural brain volumes will be determined by magnetic resonance imaging (MRI) and cortical connectivity will be quantified using resting state functional MRI and Diffusion Tensor Imaging (DTI) to evaluate integrity of and changes in white matter tracts in response to exercise and compared to healthy

CNS IRB Protocol Template (2.5.15)

volunteers. Blood will be collected to quantify the presence of biomarkers (such as VEGF, BDNF and IGF-1) and dopamine transmission, and compared to healthy volunteers. Other self-reported measures of quality of life, fatigue severity, depression and sleep quality would also be collected, and compared to healthy volunteers.

NIMH	National Institute of Mental Health	
PASAT	Paced Auditory Serial Addition Test	
PI	Principal Investigator	
PSQI	Pittsburgh Sleep Quality Index	
РТА	Post-Traumatic Amnesia	
QOLIBRI	Quality of Life after Brain Injury	
RET	Rapid-Resistive Exercise Training	
RMD	Rehabilitation Medicine Department	
RPM	Revolutions per Minute	
SAE	Serious Adverse Event	
SOT	Sensory Organization Test	
SSRT	Seashore Rhythm Test	
SWLS	Satisfaction with Life Scale	
TBI	Traumatic Brain Injury	
TBI-QOL	TBI Quality of Life	
THR	Target Heart Rate	
TMT	Trail Making Test	
ToPF	Test of Premorbid Functioning	
USU	Uniformed Services University	
USUHS	Uniformed Services University of Health	
	Sciences	
VEGF	Vascular Endothelial Growth Factors	
VO2	Oxygen Consumption	
WR	Work Rate	
WRIISC	War Related Illness and Injury Study Center	
ZCG	Impedance Cardiogram	

# 1. Introduction

Over 1.7 million people sustain a traumatic brain injury (TBI) each year, with more than 50,000 resulting in deaths [1]. Almost 80% are treated and released from emergency departments [1], however over 100,000 will further experience long-term disability [2]. TBI costs the United States approximately \$76.5 billion in direct and indirect costs [3], which includes medical costs from acute care and rehabilitation, and loss of productivity due to an inability to work.

TBI may result in physical impairments, however neuropsychological problems affecting cognition, emotional functioning and behavior are often more problematic. Particularly in those with mild TBI, subtle functional and cognitive deficits may be present that often go undetected in the acute setting or by routine clinical examination. These patients can experience drastic changes in their quality of life [4], and have difficulties returning to daily activities and work [5].

This study was initially sponsored by the Center for Neuroscience and Regenerative Medicine (CNRM) and received CNRM funds directly for the conduct of the study. CNRM sponsorship for this study has ended. The study will continue in collaboration with CNRM. Under this collaboration, the study will continue to use CNRM Core resources including the CNRM Biospecimen Repository and CNRM Informatics Data Repository.

# 1.1 Statement of the Problem

The aim of rehabilitation of individuals with chronic TBI is to restore functioning, promote neurobehavioural and psychosocial skills for re-integration into the community [6] and to return to work [2]. However, the heterogeneous mechanism of injury that occurs with TBI presents a major challenge to researchers and clinicians for optimal rehabilitative strategies and management of those with TBI. Another problem is the difficulty in comparing post-acute interventional studies because of differences in the method of data collection, outcome measures and intervention period [6]. While progress has been made in this area in recent years, research studies are needed to further develop rehabilitation strategies and our understanding of the clinical management of TBI. Considering the large proportion of patients that would benefit from rehabilitation, the need for specific interventions that would improve their quality of life is imperative.

# **1.2 Importance of the Problem**

It is well recognized that physical exercise offers many benefits in both general and clinical populations. Besides the obvious cardiovascular and metabolic adaptations that occur with exercise training, physical activity has also been related to diminished cerebral inflammation and enhanced brain plasticity [7]. Exercise increases the release and synthesis of neurotrophic factors related to cognitive functioning, neurogenesis, angiogenesis and plasticity. Among these include the brain-derived neurotrophic factor (BDNF), insulin-like growth factor (IGF-1) and vascular endothelial growth factor (VEGF).

In the animal model, deficits associated with TBI such as neuronal loss in the hippocampus [8, 9], have been found to be attenuated by exercise. A well studied and reproducible finding in the animal model is exercise-related hippocampal neurogenesis [10], which is believed to be linked to the commonly observed improvements in learning and memory following a brain injury [11, 12]. BDNF is involved in hippocampal neuronal plasticity, thus plays a major role in exercise-induced cognitive improvements [11]. Exercise stimulates BDNF gene expression in the hippocampus of the rat [13-15] and is volume-dependent, such that greater BDNF is expressed with more exercise [13]. The presence of BDNF is of primary importance, as inactivation or even the absence of an increase in BDNF is related to attenuation of the exercise induced improvements in cognitive performance in TBI rats [11, 16].

Despite encouraging findings in the animal model with exercise interventions, there are very few studies that extend this research to the TBI population. Hippocampal volume has been observed to be reduced following TBI [17-20] with greater hippocampal atrophy related to reduced memory performance [18, 20, 21]. However, there are currently no studies in the literature that have examined the effect of exercise on hippocampal volume and BDNF levels in patients with TBI. Studies in other populations such as normal aging and schizophrenia have demonstrated exercise-induced increases in hippocampal volume [22, 23], while exercise training has been associated with increased resting BDNF levels in young adults [24, 25]. The combined body of evidence from TBI animal studies and those of other disease states in humans suggest that this line of research needs to be extended to the TBI population.

Review of the current literature on exercise interventions is also conflicting, with results being equivocal or the lack of studies on specific interventions making it unreasonable to draw conclusions. For instance, cognitive function in TBI patients was found to be either improved [26] or unchanged [27] following 4 weeks of exercise training, while fewer cognitive symptoms were reported by TBI patients that were considered to be exercisers based on self-reported physical activity [28]. A major problem in these studies is that the exercise was mostly unsupervised [27], or based on the subject's reported perceived exertion [26] or exercise habits [28].

The intensity of exercise that produces the greatest benefit in patients with TBI is also currently unknown. While aerobic exercise training is generally viewed as having the greatest effect from a cardiovascular and metabolic perspective, this level of intensity may not be appropriate for all individuals with TBI. Exercising at a higher level of intensity is related to greater cardiorespiratory fitness, however the effect of exercise on cognitive performance is not strictly dose-dependent. Improved cardiorespiratory fitness is not always associated with greater cognitive improvements [29]. Indeed, exercise in the light to moderate intensity domain has been suggested as being ideal for stimulating hippocampal neurogenesis [30]. Considering that individuals with TBI experience wide variability at the cellular, macro and outcome-level, the exercise prescription should take into account these concerns [7]. Currently, there is not enough research in this area to warrant recommendations for intensities of physical exercise for optimal rehabilitative outcomes for patients with TBI.

The existing data from the literature with regards to exercise training in chronic TBI patients are sparse. There is a need for clinical research with an integrative approach that examines neuroplastic changes that occur concurrently with objective behavioural measures across multiple functional domains.

#### **1.2.1 Preliminary Results**

Two recent pilot studies were performed in the Rehabilitation Medicine Department in patients with chronic TBI. The findings are discussed below:

# 11-CC-0088: Effect of aerobic exercise training on cardiorespiratory function in patients with TBI

In this study, results from 10 subjects (age,  $33 \pm 7$  years; mean  $\pm$  SD) suggest that patients with TBI are able to demonstrate improvements in cardiorespiratory function with a training regimen that is generally prescribed to the general population. Specifically, patients increased their time to volitional fatigue, attained higher peak O2 consumption and demonstrated improved aerobic capacity (Table 1). Patients exercised on a treadmill for 30 minutes at an intensity considered to be "vigorous" (i.e., heart rate range of 70 - 80 % heart rate reserve), 3 times a week for 12 weeks. Despite the challenging training regimen, patients were able to adhere and maintain their target intensity throughout the session duration (Table 2). These findings have been published and are available ahead of print [31].

CPET Variables	Pre	Post	$\Delta$	P-Value
Time to peak $VO_2(s)$	982 (113)	1066 (142)	+84 (45)	< 0.001
Peak VO 2 (ml/kg/min)	37.1 (8.2)	40.2 (8.1)	+3.1 (2.4)	0.003
Peak WR (W)	324 (90)	383 (104)	+59 (48)	0.005
Time at AT (s)	556 (92)	662 (92)	+106 (63)	< 0.001
VO 2 at AT (ml/kg/min)	18.9 (4.1)	22.5 (3.5)	+3.6 (2.1)	< 0.001

#### Table 1. Results of the Cardiopulmonary Exercise Test

Abbreviations: VO2, oxygen consumption; WR, work rate; AT, anaerobic threshold

Table 2. Sum	mary of Ae	erobic Exer	cise Train	ning
--------------	------------	-------------	------------	------

	Group Mean
Adherence, %	93 (4)

Average training heart rate, bpm	155 (7)
% HRR	78 (2)
Total AET time, min	1005 (38)

Abbreviations: HRR, heart rate reserve; AET, aerobic exercise training

Neuropsychological testing was also performed on 7 consecutive subjects and these results are available ahead of print [32]. Significant improvements (p < 0.05) were observed for processing speed and executive functioning following AET, as measured with the Trail Making Test A and B (Figure 1). Overall cognitive function, including those specific to delayed memory and visuospatial/constructional was also improved after the exercise intervention (Figure 2).

**Figure 1.** Time taken to complete the Trail Making Test (TMT) A and B (left), with standardized t-scores (right) shown before and after AET.

**Figure 2.** Averaged index scores for the Repeatable Battery for Assessment of Neuropsychological Status (R-BANS) at pre- and post-AET. Symbol with lines indicate the mean for a standardized sample based on age (20 – 49 years) and education level (> High school).

Results suggest that patients with TBI are able to safely perform intense aerobic exercise and gain not only physical benefits but likely mental improvements as well.

**Figure 4.** Changes in dual task word generation and mean latency of the Motor Control Task between pre and post RET.

While no significant changes in cognition were observed, 7 of the 10 patients scored within the normal range at baseline which demonstrates an absence of cognitive impairment in the majority of patients enrolled in this study. Therefore, little improvement would be expected from this subset of patients.

Both these pilot studies revealed improvements in different aspects of functioning in a TBI population using different exercise intensities. Cardiorespiratory fitness and cognitive function was improved with vigorous intensity exercise training, while balance and motor control was improved with moderate levels of exercise intensity. Likely activation of different mechanisms/pathways occurred to result in the observed improvements in the respective studies. However, specific outcomes were selected for each study and there was limited overlap in the measured outcomes. Whether similar improvements would be observed regardless of exercise intensity is therefore unknown. Considering the wide range of symptoms and deficits a patient with TBI may experience, the optimal type and intensity of exercise may also differ depending on the patient's level of impairment.

# 2. Study objectives

The broad objective of this study is to determine the effectiveness of two types of exercise training in patients with non-penetrating TBI for improving cognitive performance, balance, physical fitness, fatigue severity and other behavioral or quality of life outcomes. This study will also measure structural and functional changes in the brain and specific biomarkers known to be involved in brain plasticity as well as to examine genetic factors that may affect responsiveness to the training. This study may also identify the intensity of exercise training that is more highly associated with specific cognitive, functional and structural improvements.

The 2 exercise regimens to be used are as follows:

#### Aerobic Exercise Training (AET)

Aerobic exercise will be performed using an elliptical trainer. Exercise intensity would be vigorous ( $\sim 70 - 80\%$  of maximal VO2) and similar to a previous pilot study (11-CC-0088). A target heart rate range will be used to ensure vigorous intensity is maintained throughout the training session. While treadmill walking was used previously (in 11-CC-0088), adjustment of the resistance on the elliptical trainer will allow for aerobic exercise to be safely achieved with this mode.

#### Rapid-Resistive Exercise Training (RET)

CNS IRB Protocol Template (2.5.15)

Rapid, reciprocal exercise will be performed using an elliptical trainer, which allows for safe fast speed training. Similar to the previous study (10-CC-0150), this type of training will involve rapid movement and coordination of all four extremities. Emphasis will be placed on increasing speed, however resistance can be increased to keep the level of exercise at a light to moderate intensity. Exercise intensity would not exceed ~ 50% of maximal VO2 (moderate intensity).

The objectives of this study are:

- Primary To evaluate the effects of exercise training intensity on cognitive function in patients with TBI
- Secondary To evaluate the effects of exercise training intensity on balance, physical fitness and quality of life in patients with TBI
- Secondary To evaluate the effects of exercise training intensity on structural and functional changes in the brain of patients with TBI
- Secondary To examine the relationship between cognitive, behavioral, and motor outcomes and brain imaging, biomarker and genetic outcomes or variables
- Secondary To examine structural/functional brain differences, blood biomarkers and a subset of cognitive and self-reported outcomes between patients with TBI and healthy volunteers within the same age range

Since the direct effects of physical exercise are well known, the primary focus here is on the effects of exercise on cognitive function and on brain connectivity. While we anticipate that exercise regardless of intensity will improve cognitive and behavioral outcomes, we anticipate that the effects will be greater for the aerobic training group such that when the results are analyzed separately for each exercise condition, only the aerobic group will demonstrate a significant change in the primary outcome measure. Study outcomes such as brain imaging, blood biomarkers, cognitive performance and selfreported questionnaires in patients with TBI will also be compared to a healthy volunteer sample matched to the TBI cohort for sex and age within 5 years.

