# 3. Subjects

### 3.1 Study populations

This study will recruit a maximum of 80 adults (aged between 18 and 79 years old) with non-penetrating TBI and a comparison group of up to 20 healthy volunteers matched to the TBI cohort for sex and age within 5 years. The healthy volunteers will only undergo brain imaging assessments, blood collection and a subset of questionnaires and neuropsychological testing. The healthy volunteers will not participate in the intervention phase. Withdrawals or dropouts will be replaced to have at least 20 subjects with TBI in each group to complete the second assessment visit. An eligibility checklist is included in Appendix 3A and B.

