### 7.3 Criteria for Individual Subject Withdrawal

Federal regulations require that subjects may withdraw from participation in the study at any point without prior notice and without adversely affecting their medical management, educational or employment status. At the time of withdrawal, subjects will also be able to withdraw their data from the study. The study investigators may also withdraw subjects from the study for medical, administrative or issues of non-compliance. If the subject experiences a clinically significant worsening of mood or behavioral symptoms (not an emergency), she/he will be removed from the study and the physician and/or neuropsychologist will ask the subjects if they would like them to make a referral for further outside evaluation and treatment. Any psychiatric emergency would also be cause for withdrawal from the study and will prompt immediate psychiatric evaluation at NIH.

During the course of the study, subjects will be instructed to continue with their current care. Alterations of care must not include changes in therapy, exercise regimen or medication that would potentially alter cardiorespiratory capacity, mood, or cognitive or motor abilities, or the ability to achieve a training adaptation measurable by the methods used in this study. If the subject does make these types of changes, they will be administratively withdrawn from the study. If a subject misses an assessment and is unable to reschedule it within four weeks, they will be withdrawn from the study. We will replace all who withdraw or were withdrawn from the study for the above reasons.

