# 9. Statistical Analysis

### 9.1 Analysis of data

The primary analysis is a mixed model (with time as the within-subject factor and exercise group as the between subject factor) analysis of variance (ANOVA) which will be used to determine significant differences in the primary (ANOVA) and secondary outcome variables (MANOVA by outcome category – i.e. motor, cognitive, behavioral, etc – to help control for multiple comparisons) as a result of exercise. Therefore, the data will include the time points immediately pre and post exercise for all subjects. We are interested in both main effects for time and exercise as well as potential interaction effects between exercise group and time.

All subjects completing the protocol and not withdrawing or presenting off study criteria will be included in the analyses. Secondary analyses related to protocol adherence and other aspects of feasibility are anticipated. Estimation of the necessary and sufficient sample size was calculated for a large effect change in the main outcome variable, pre- to post-training change in executive functioning. Significance will be set at p < 0.05.

While we do not anticipate that subjects will improve over time in the absence of exercise, we have included a waitlist control to evaluate this, and we will compare the amount of change over time in the control group versus the exercise group that were not waitlisted using an independent t-test. Also for the exercise group that was not waitlisted, there will be a three month follow up period evaluated to determine whether there is any change compared to the end of the exercise period using paired t-tests.

The change in aerobic capacity and fast elliptical speed will be correlated with changes in the other outcomes measures. Baseline dopamine transmission scores will also be correlated with all motor outcomes using linear regression.

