### 9.2 Power analysis

Based on findings in the pilot study (11-CC-0088) [32], calculations indicate that 20 subjects would be needed to detect a significant difference in the main outcome variable of executive functioning with Trail Making Test B for an  $\alpha = 0.05$  and  $\beta=0.05$ . Therefore, 20 subjects in each of the conditions are expected (total 60 subjects). Attrition is approximately one-third for an exercise training protocol, so we predict recruitment of 80 subjects with non-penetrating TBI to have at least 20 subjects in each condition have completed the second assessment visit.

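### The TBI-versus-healthy-volunteer comparison has no stated TBI visit, and the completer-only rule in section 9.1, read literally, discards baseline TBI data for later events

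*Combined protocol and SAP*

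**What the plan says.** **The objective.** Section 2 lists, as its last secondary objective, differences between patients with TBI and healthy volunteers in brain structure and function, blood biomarkers, and some cognitive and self-reported outcomes. It closes by repeating that "blood biomarkers, cognitive performance and selfreported questionnaires in patients with TBI will also be compared to a healthy volunteer sample". Section 8.2 repeats the comparison and calls the volunteers a reference sample. Just before that, it says secondary analyses may include comparisons of baseline measures.

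**The visits.** The Precis gives volunteers "a subset of the cognitive and behavioral testing at a single time-point", and section 4.1 confirms one visit. Under section 4.4, TBI subjects are assessed at baseline, 3 months and 6 months. The baseline assessment comes before randomisation (section 4.1). No section says which TBI visit enters the volunteer comparison.

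**The analysis set.** Section 9.1 does not mention healthy volunteers. Its one population rule is "All subjects completing the protocol and not withdrawing or presenting off study criteria will be included in the analyses".

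**How TBI subjects leave.** Section 4.4.7 ties continued eligibility to completing 30 of 36 sessions. Section 7.3 removes subjects for non-compliance, for certain changes of therapy, medication or exercise regimen, and for an assessment missed and not rescheduled in time. It also provides for removal "If the subject experiences a clinically significant worsening of mood or behavioral symptoms". Subjects who withdraw may also withdraw their data.

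**The Precis imaging sentence.** Diffusion tensor imaging is to "evaluate integrity of and changes in white matter tracts in response to exercise and compared to healthy" volunteers.

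**The concern.** Every enrolled TBI subject with a baseline assessment has already supplied the value this objective needs. Whether that subject later attends enough sessions has no bearing on how he or she differed from a healthy person at entry. If the completer rule governs, post-baseline events decide whose baseline counts.

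The filter acts on one side only, because volunteers finish at their single visit. Part of it also touches what is being compared: the depression and symptom inventories are given to volunteers too (section 4.4.2), and worsening mood is a ground for removing a TBI subject. The TBI group entering the comparison may therefore not represent the TBI group enrolled.

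The unnamed visit is a separate gap. With three TBI assessments and one volunteer assessment, the same data allow several different contrasts, and the plan does not say in advance which one answers the objective. If a follow-up visit were chosen, the TBI value would carry repeat testing and, for exercisers, training. Section 4.5 itself acknowledges practice effects.

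**Working it through.** **Inputs**
- Enrolment ceiling: "This study will recruit a maximum of 80 adults" with TBI (section 3.1).
- Planned completers: 20 per condition, 60 in total (section 9.2).
- Attrition: "Attrition is approximately one-third for an exercise training protocol, so we predict recruitment of 80 subjects with non-penetrating TBI" (section 9.2).
- Volunteers: up to 20 (section 3.1). I take 20.
- Assumptions: equal SDs in the two groups, matching ignored, and the outcome SD as the unit. The plan gives no SD for these outcomes.

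**Step 1. The plan's own recruitment figure**
- 60 × (1 + 1/3) = 80 reproduces the stated figure.
- Leaving 60 completers after a one-third loss would take 60 / (1 − 1/3) = 90.
- Recruiting 80 to leave 60 implies a loss of 1 − 60/80 = 25%.
- A one-third loss from 80 leaves 80 × 2/3 = 53.3, about 53.

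The plan's figures disagree, so I carry both: 25% (60 remain) and one-third (about 53 remain).

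**Step 2. Precision**

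SE = SD × √(1/20 + 1/n), with n the number of TBI subjects. Detectable difference at 80% power, two-sided 0.05 (normal formula) = (1.96 + 0.84) × SE.

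| TBI subjects used | SE (SD units) | Rise in SE | Detectable difference (SD) | Power at 0.5 SD | Power at 0.8 SD |
|---|---|---|---|---|---|
| 80, all baselines | √(0.05 + 0.0125) = 0.250 | – | 0.70 | 52% | 89% |
| 60, planned completers | √(0.05 + 0.0167) = 0.258 | 3% | 0.72 | 49% | 87% |
| 53, one-third loss | √(0.05 + 0.0189) = 0.262 | 5% | 0.735 | 48% | 86% |

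The 20 volunteers contribute 0.05 to the variance whatever happens on the TBI side, so precision hardly moves.

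**Step 3. Selection**

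Let p be the fraction leaving and g the amount by which leavers' baseline deficit exceeds that of completers.
- Full-cohort deficit = (1 − p) × completer deficit + p × leaver deficit.
- Completer estimate minus full-cohort deficit = −p × g.

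The documents give no baseline profile of leavers. I assume g between −0.5 and +0.5 SD:
- p = 1/4: 0.25 × 0.5 = 0.125, so the error runs from +0.125 to −0.125 SD.
- p = 1/3: 0.333 × 0.5 = 0.167, so the error runs from +0.17 to −0.17 SD.

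At the edge of that range the error is about half of one SE (0.125 / 0.258 = 0.48) to two-thirds of one (0.167 / 0.262 = 0.64). Smaller differences scale down in proportion; at g = ±0.2 SD the error is 0.05 to 0.07 SD.

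**The case against.** The strongest reply is that section 9.1 was not written with volunteers in mind. Its population sentence follows the paragraph on the pre- and post-exercise model, and its own paragraph goes on to adherence and to sample size for training change. Section 8.2 also mentions baseline comparisons immediately before the volunteer sentence, so a sensible analyst might use all baselines anyway. This is fair, and it makes the issue one of literal reading. It does not remove it: the baseline wording is permissive, the population rule has no exception, and no other rule exists.

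Four stronger readings are tempting, and the documents do not support them.
- *The volunteer comparison is tied to exercise response.* Only one Precis sentence, on imaging, can be read that way, and it can also be read as comparing tract integrity with volunteers. The objective in section 2 has no such link, and volunteers seen once have no change to compare.
- *TBI deficits are understated.* That needs leavers to be worse at baseline. Withdrawal also follows pregnancy, administrative reasons, therapy changes and scheduling failures, none of which need mark a worse baseline.
- *A third of the TBI data is lost, with serious loss of power.* The planned counts give 25%, and on either figure power falls by no more than about 4 points at the differences shown.
- *Retest gains contaminate the comparison.* No section says follow-up TBI values will be used. Some volunteers may also have been tested before, since section 4.1 allows recent assessments from related studies to be reused.

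**Conclusion.** The point holds as a gap in specification combined with an ill-fitting rule. The plan does not fix the TBI visit for a declared secondary objective, and its only analysis-set rule, taken at its word, removes pre-randomisation data for post-baseline reasons that affect one group alone.

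The loss is 25% of enrolled TBI subjects on the planned counts, or about a third at the stated attrition. It could differ if completing the protocol means reaching the 6-month visit, for which no loss is given. The precision cost is small, 3–5% on the SE. Selection bias is possible, with sign unknown and size up to about 0.125–0.17 SD. That range rests wholly on the assumed limit of 0.5 SD between leavers and completers.

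The randomised primary comparison is unaffected by this point. The change is still worth making, because the better analysis set is already in hand and naming it in advance prevents a choice of visit after the results are seen.

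**What to change.** - In sections 8.2 and 9.1, state that the healthy-volunteer comparison uses baseline (pre-randomisation) values of all enrolled TBI subjects with a baseline assessment. Make this apply regardless of later completion, and exempt it explicitly from the completer rule.
- Add one exception: data that a subject withdraws under section 7.3.
- Clarify the Precis imaging sentence so that change in response to exercise is judged against the randomised waitlist. Label any comparison of follow-up TBI values with the once-tested volunteers as descriptive only.

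The cost is wording in the Precis and two sections. The baseline assessments are already in the schedule, so there is no extra visit, test or subject.
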